## 4. Study Objectives

### 4.1. Phase I

The primary objective is:

- To determine the maximum tolerated dose (MTD) of AK-01 as monotherapy in patients with locally advanced or metastatic solid tumors.

The secondary objective is:

- To evaluate the tolerability and overall safety profile of AK-01.

The exploratory objectives are:

- To evaluate the pharmacokinetic (PK) and pharmacodynamic (PD) characteristics of AK-01.
- To compare PD markers of AK-01 target engagement in skin biopsies.
- To assess preliminary evidence of AK-01 anti-tumor activity.

### 4.2. Phase II

The primary objective is:

- To evaluate the objective response rate (ORR) of AK-01 in up to 4 cohorts of locally advanced or metastatic solid tumor types of interest.

The secondary objectives are:

- To evaluate the tolerability and overall safety profile of AK-01.
- To evaluate the PK and PD characteristics of AK-01.

The exploratory objectives are:

- To evaluate the effect of AK-01 on other clinical endpoints in these indications.

- To evaluate the efficacy of AK-01 in patients with locally advanced or metastatic solid tumor types of interest with different molecular profiles.

## 5. Study Design

### 5.1. Brief Summary

#### 5.1.1. Phase I

In Phase I, up to 30 patients with locally advanced or metastatic tumors for whom no treatment of higher priority exists will be enrolled. The 3 + 3 method will be used for increasing, maintaining, or decreasing the dose of AK-01. Dose-limiting toxicities (DLTs) will be evaluated for each cohort from the time of first administration of AK-01 through the first 21-day cycle. The frequency of DLTs in the previous cohort will determine whether the dose of the subsequent cohort will increase, decrease, be maintained, or stop. Dose escalation rules are described in detail in the Protocol, Section 3.1.3.

Enrollment cannot begin in a new cohort until the Safety Assessment Committee (SAC) has met to discuss the data from the previous dose level. Safety data will be the primary criteria for both the decision to dose escalate and for selecting the dose to be administered in the next cohort. The 25 mg BID dose has been chosen as the dose for Phase II. Determination of the phase II dose is describe in detail in the protocol, Section 1.3.

Following Cycle 1, if no DLT-equivalent toxicity is experienced, a given patient's dose may be maintained or escalated (for details, see the Protocol, Section 3.1.4). Any patient who continues in the study following Cycle 1 will be assessed for toxicity and tolerability throughout their participation. The safety and tolerability of dose escalation in these patients may guide dose decisions for new cohorts.

Following completion of Cycle 1, dosing may continue in 21-day cycles until disease progression if the patient is receiving benefit and is experiencing no severe toxicity in the opinion of the investigator.

#### 5.1.2. Phase II

Phase II will evaluate the preliminary efficacy of AK-01 in up to 4 cohorts; initially in patients with locally advanced or metastatic small-cell lung cancer (SCLC) and breast cancer (BC), and subsequently, at sponsor's discretion, in patients with TNBC, SCC-HN, and OT. Up to 30 patients may be enrolled in each cohort, giving an estimated total of 120 patients. Since AK-01 is an experimental treatment, patients will need to have failed standard of care therapies (i.e., platinum-

based therapy for SCLC; hormone therapy and a CDK4/6 inhibitor for BC; relapsed/resistant TNBC patients; standard therapy for HPV associated SCC-HN) before being enrolled in this trial.

All open cohorts in Phase II may begin enrollment concurrently and will be dosed at 25 mg BID. Dose increases will not be allowed in Phase II.

After Cycle 1, dosing of AK-01 may continue in 21-day cycles until disease progression if the patient is receiving benefit, and is experiencing no severe toxicity in the opinion of the investigator.

Dose modifications for toxicity for both phases are described in the Protocol, Section 3.3.2.

### 5.1.3. Randomization and Blinding

This is a non-randomized, open label study.

## 6. Study Endpoints

### 6.1. Efficacy Endpoints Definitions

Tumor response will be assessed by a radiologist following the Response Evaluation Criteria in Solid Tumors (RECIST) guidelines v.1.1.1.

#### Objective Response Rate

Objective response rate (ORR) is defined as a proportion of responders (CR+PR) of those patients whose disease at baseline is assessable by RECIST v 1.1.1.

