## **6.7. Efficacy Evaluations**

### *6.7.1. Radiographic Tumor Assessment*

Tumor response will be assessed by a radiologist following the RECIST guidelines v. 1.1 (Appendix 10). The schedule of tumor assessments will be maintained independent of any treatment schedule delays or changes. For any patient who discontinues the study for reasons other than radiographic progression (e.g., symptomatic progression, unacceptable toxicity), a tumor assessment will be performed at the Discontinuation visit only if  $\geq 4$  weeks has elapsed since the last tumor assessment. An unscheduled tumor assessment will be obtained in such patients if a Discontinuation visit will not be conducted. Patients who discontinue the study for reasons other than radiographic progression will be followed according to standard of care following discontinuation.

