#### Best Overall Response

Best overall response (BOR) is defined as the best response across all time point responses observed while on study treatment (for example, a patient who has stable disease (SD) at first assessment, partial response (PR) at second assessment, and progressive disease (PD) on last assessment has the BOR of PR). Only time point responses prior to PD or initiation of additional treatment (e.g. surgery, radiotherapy) will be included in the determination of BOR. When SD is believed to be best response, it must be observed at minimum 4 weeks since the Treatment start date to be considered for the BOR.

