#### Disease Control Rate

Disease control rate (DCR) is defined as a proportion of patients with BOR of SD, PR or complete response (CR) of those patients whose disease at baseline is assessable by RECIST v 1.1.1. Confirmation of CR and PR is required, as specified in RECIST v 1.1 guidelines [3], Table 3. The confirmatory scan in such cases must be performed at minimum 4 weeks-5 days, that is 23 days later.

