### Duration of Objective Response

Duration of response (DOR) is applicable only for partial or complete responders. It is defined as the time from the date of a documented treatment response (CR or PR) to the date of an event defined as the first documented progression or death due to any cause, whichever is earlier. For clarity, the start date will be determined by the initial assessment of CR or PR, not the date of confirmation of CR or PR. Patients without the event will be censored at the date of the last adequate tumor assessment (i.e. the assessment with evaluable overall response). Patients without any further adequate tumor assessments will be censored on the day of the response.

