## 9.6. Analyses of Efficacy

### 9.6.1. Phase II Primary Objective

The primary endpoint of phase II is ORR. The primary statistical hypotheses

$$H_0: \text{ORR} \leq 0.05$$

will be tested against an alternative

$$H_A: \text{ORR} > 0.05$$

by the means of a one-sided exact binomial test for a single proportion at a significance level of 0.05. See Section 9.3.1 for details on the statistical test. No multiple testing adjustment will be applied. The ORR will be presented with an exact one-sided 95% confidence interval (Clopper & Pearson). The analysis will be performed in the FAS as well as in Efficacy evaluable analysis set. That means, if the analysis set includes patients with missing baseline assessments, non-measurable disease at baseline (though this would be a protocol deviation) or no evaluable post-baseline

assessments, they will be counted in the denominator and not in the numerator. The ORR will be summarized and tested by cohort.

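### The 23-day confirmation rule for CR and PR is stated only under disease control rate and is not carried to the primary ORR or to BOR

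*SAP*

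**What the plan says.** Four places in the SAP bear on what counts as a response.

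- **ORR (6.1), the Phase II primary endpoint:** "Objective response rate (ORR) is defined as a proportion of responders (CR+PR) of those patients whose disease at baseline is assessable by RECIST" v1.1. No confirmation condition is stated.
- **BOR (6.1):** "Best overall response (BOR) is defined as the best response across all time point responses observed while on study treatment". The worked example goes from SD to PR to PD and gives a BOR of PR. It mentions no confirming scan, but it does not rule one out.
- **DCR (6.1), exploratory:** DCR is built on BOR. Here, and only here, the SAP says "Confirmation of CR and PR is required, as specified in RECIST v 1.1 guidelines [3], Table 3", and "The confirmatory scan in such cases must be performed at minimum 4 weeks-5 days, that is 23 days later".
- **Primary analysis (9.6.1):** patients with no baseline assessment, non-measurable disease or no evaluable post-baseline assessment are handled explicitly: "they will be counted in the denominator and not in the numerator". An unconfirmed CR or PR is not on that list.

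The definition of duration of response (SAP 6.1) presupposes confirmation, since "the start date will be determined by the initial assessment of CR or PR, not the date of confirmation of CR or PR". SAP 7.9 derives the response at each assessment programmatically and mentions no confirmation step.

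In the protocol, note r of Appendix 1 schedules a confirmatory scan at 4 weeks ± 5 days for every CR or PR. The ORR wording in sections 3.6 and 8.1.6 does not say whether only confirmed responses count.

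**The concern.** A programmer who works from the ORR, BOR and 9.6.1 text would count a single PR assessment as a response. One who takes the sentence under DCR as governing all CR and PR would not. The two counts differ for any CR or PR without a qualifying second scan. There are two plain routes to that.

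- The response is not maintained at the confirmatory scan, for example PR followed by SD or PD.
- The patient stops early and no second scan is done. For a patient who stops for a reason other than radiographic progression, protocol 6.7.1 says "a tumor assessment will be performed at the Discontinuation visit only if" at least 4 weeks have passed since the last one, and Appendix 1 note u says the same in substance. Note r states no exception to the confirmatory scan, so this is a possible route, not a certain one.

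The trial is open-label and single-arm, and each cohort is tested on a handful of responders. If the reading is left open until the data are visible, the primary result of a cohort could depend on a choice made after seeing it.

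**Working it through.** **Inputs.** Null ORR 5%, one-sided exact binomial test, level 0.05, no multiplicity adjustment (SAP 9.6.1). Alternative 20% and cohort sizes 15 and 20 (protocol 3.6 and Table 2). Maximum cohort size 30 (protocol 3.6). Confirmation interval: 28 − 5 = 23 days minimum (SAP 6.1, DCR); protocol window 28 ± 5, that is 23 to 33 days (Appendix 1 note r).

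**Step 1. Critical values and the plan's own power.** The critical value c is the smallest count with P(X ≥ c | N, 0.05) ≤ 0.05. Power is P(X ≥ c | N, p).

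| N | c | attained level | power at p = 10 / 15 / 20 / 25 / 30% | protocol Table 2 |
|---|---|---|---|---|
| 15 | 3 | 0.0362 | 18.4 / 39.6 / 60.2 / 76.4 / 87.3% | 18 / 40 / 60 / 76 / 87% |
| 20 | 4 | 0.0159 | 13.3 / 35.2 / 58.9 / 77.5 / 89.3% | 13 / 35 / 59 / 78 / 89% |
| 30 | 5 | 0.0156 | 17.6 / 47.6 / 74.5 / 90.2 / 97.0% | not given |

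Table 2 is reproduced, so the test is understood as the protocol intends.

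**Step 2. Effect of one response.** The p-value is P(X ≥ x | N, 0.05). For N=15 and x=2: 1 − 0.95^15 − 15 × 0.05 × 0.95^14 = 1 − 0.4633 − 0.3658 = 0.171. For x=3, subtract P(X=2) = 0.1348, which gives 0.036. The one-sided 95% Clopper-Pearson lower limit is the 0.05 quantile of Beta(x, N − x + 1).

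| N | responders | p | lower limit |
|---|---|---|---|
| 15 | 2 vs 3 | 0.171 vs 0.036 | 2.4% vs 5.7% |
| 20 | 3 vs 4 | 0.0755 vs 0.016 | 4.2% vs 7.1% |
| 30 | 4 vs 5 | 0.061 vs 0.016 | 4.7% vs 6.8% |

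At N=15 and N=20 the critical count is also the protocol's 20% observed-rate bar (3/15 and 4/20). At N=30 it is not: 5/30 is 16.7% and the bar needs 6/30 (p = 0.003), so there the change from 4 to 5 affects the SAP test only.

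**Step 3. Feasibility.** A scan done inside the scheduled 23 to 33 day window already meets the 23-day minimum. Applying the rule to ORR needs no new scan.

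**Step 4. Possible cost in power (illustration only).** Suppose the 20% alternative was meant to include unconfirmed responses and a share f of first responses does not confirm. Power becomes P(X ≥ c | N, 0.20 × (1 − f)). The documents give no f. Taking 10% to 40% as an assumed range:

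| N | f = 0 | f = 10% | f = 40% |
|---|---|---|---|
| 15 | 60% | 52% | 27% |
| 20 | 59% | 50% | 21% |
| 30 | 74% | 65% | 29% |

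If the 20% already means confirmed responses, Table 2 stands unchanged.

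**The case against.** The best case on the other side is that confirmation is already there when SAP 6.1 is read as a whole. The sentence under DCR is worded generally. DCR is defined through BOR and counts SD, PR and CR alike, so a rule about confirming CR and PR does little work there unless it governs how BOR is classified. Duration of response refers to a confirmation date, and the protocol schedules a confirmatory scan for every response. In addition, response is assessed by RECIST, and the places where an unconfirmed response would naturally be classified cannot be checked: protocol Appendix 10 is redacted, and the guideline table that the SAP cites is an outside source.

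Much of this stands. It makes confirmed response the likelier intention, and it means that a reader who infers a flat contradiction between the BOR and DCR definitions goes further than the text allows. It does not close the gap. None of these places makes confirmation a condition of the primary ORR, and 9.6.1 lists who stays out of the numerator without naming unconfirmed responses.

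A reader might also infer that the protocol's 4-month durability criterion (3.6) would remove unconfirmed responses anyway. The documents do not support that. Section 3.6 does not define durability, and the SAP runs duration from the first CR or PR to progression or death. A PR followed by SD at the confirmatory scan and PD five months after the PR would have a duration above 4 months without ever being confirmed. The SAP test does not include the durability criterion in any case.

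Finally, sensitivity to one responder is a property of any cohort of 15 to 30. That is true, and it is why the responder rule has to be fixed in advance.

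**Conclusion.** The point holds as a gap in the definition of the primary endpoint and should be fixed before lock. As written, the primary numerator can include unconfirmed CR or PR, and one such response can move a cohort across the 0.05 line at N=15, 20 or 30. The arithmetic rests only on the stated test. The practical effect depends on how many responses lack a qualifying second scan, which the documents do not say.

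Two stronger readings are not supported. One is that the type I error is inflated. That would need a non-confirmation rate and a statement that the 5% null refers to confirmed responses, and neither is given. The other is to put a probability on the two readings disagreeing. At a true ORR of 20%, a cohort lands exactly on its critical value with probability 25%, 22% and 17% at N=15, 20 and 30. Those figures are only the chance of being where the loss of one response would reverse the test. They are not the chance that the readings differ.

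**What to change.** Before database lock:

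1. In SAP 6.1 (ORR and BOR) and 9.6.1, state that the confirmation rule now under DCR applies: a second scan at least 23 days after the first CR or PR.
2. State that an unconfirmed CR or PR, including one with no second scan, is in the denominator and not in the numerator, and how it is classified for BOR.
3. Add the confirming scan to the BOR example.
4. Report unconfirmed ORR as a sensitivity analysis.
5. State whether the 5% and 20% rates refer to confirmed responses. The documents do not say, so this is a question for the sponsor. If the 20% was an unconfirmed rate, restate the power.

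The cost is SAP wording and programming. The downside is that the observed ORR may be lower than under the unconfirmed count.

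A separate, minor point on an exploratory endpoint: protocol 8.1.6 defines disease control, SD included, over two consecutive scans. The SAP accepts one SD assessment: "When SD is believed to be best response, it must be observed at minimum 4 weeks since the Treatment start date". SAP section 2 does not list this as a change. Reconcile the two definitions or declare the change there.

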#### Best Overall Response

Best overall response (BOR) is defined as the best response across all time point responses observed while on study treatment (for example, a patient who has stable disease (SD) at first assessment, partial response (PR) at second assessment, and progressive disease (PD) on last assessment has the BOR of PR). Only time point responses prior to PD or initiation of additional treatment (e.g. surgery, radiotherapy) will be included in the determination of BOR. When SD is believed to be best response, it must be observed at minimum 4 weeks since the Treatment start date to be considered for the BOR.

#### Disease Control Rate

Disease control rate (DCR) is defined as a proportion of patients with BOR of SD, PR or complete response (CR) of those patients whose disease at baseline is assessable by RECIST v 1.1.1. Confirmation of CR and PR is required, as specified in RECIST v 1.1 guidelines [3], Table 3. The confirmatory scan in such cases must be performed at minimum 4 weeks-5 days, that is 23 days later.

### Duration of Objective Response

Duration of response (DOR) is applicable only for partial or complete responders. It is defined as the time from the date of a documented treatment response (CR or PR) to the date of an event defined as the first documented progression or death due to any cause, whichever is earlier. For clarity, the start date will be determined by the initial assessment of CR or PR, not the date of confirmation of CR or PR. Patients without the event will be censored at the date of the last adequate tumor assessment (i.e. the assessment with evaluable overall response). Patients without any further adequate tumor assessments will be censored on the day of the response.

### Progression Free Survival

Progression free survival (PFS) is defined as the time from the date of first study drug treatment until the date of radiographic documentation of disease progression (as defined by RECIST v 1.1) or death due to any cause, whichever is earlier. Patients without progressive disease or death will be censored at the date of the last adequate tumor assessment. Patients with disease progression or death after missing (or not evaluable)  $\geq 2$  consecutive post baseline tumor assessments will be censored at the date of the last adequate tumor assessment before the missed (or not evaluable) tumor assessments. Technically, events after  $\geq 2$  missing assessments are identified as events that meet either of the following

- there was no preceding post-baseline adequate tumor assessment and the event occurred more than 1 week of the last dose in Cycle 4
- the first post-baseline assessment was performed within 1 week of the last dose in Cycle 2 and then the event occurred more than 10 weeks of the last dose in Cycle 4
- the event occurred more than 19 weeks (2x9 weeks + the allowed assessment window) after the last adequate tumor assessment.

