### 5.2.2. Dose and Regimen

AK-01 will be administered twice daily, every day of a 21-day cycle. Patients will be dosed continuously: there will be no dosing holiday between cycles.

In Phase I, the dose of AK-01 will be between 25-75 mg BID per day (see [Table 3](#)). Patients in the first cohort of Phase I will receive 25 mg BID AK-01. Following a review of safety and other relevant data from this cohort, the SAC will decide on the dose for the subsequent cohort based on [Table 3](#). Following DLT or completion of Cycle 1, dosing for a given patient will be based on individual safety and tolerability.

For Phase II, the sponsor and SAC has established the dose of AK-01 as 25mg BID.

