  - q. PK sampling will be performed in Cycle 1 of both Phase I and II at the following time points relative to the first dose on Day 1 and Day 15: 0 hours (pre-dose) and 1, 2, 4, 6, and 8-12 hours post-dose. Additional trough samples will be obtained prior to dosing on Day 2 and Day 8 of Cycle 1. The sampling schedule may be modified following review of PK data from the first cohort in Phase I to optimize collection times. A PK sample will also be obtained at the Discontinuation visit. A maximum of 3

additional PK samples may be drawn at other time points during the study, if warranted and agreed upon by both the investigator and the sponsor.

- r. A CT scan with IV contrast and assessment of tumor response by RECIST (v. 1.1, see Appendix 10) will occur within 1 week of the last dose of Cycle 2 and Cycle 4, and every 9 weeks ( $\pm$  1 week) thereafter for the duration of treatment. The schedule of tumor assessments will be maintained independent of any treatment schedule delays or changes. All CT scans will include the chest, abdomen and pelvis. For each tumor assessment, the date, method, and response evaluation will be recorded. Tumor response will not be evaluated at the screening CT scan (collected as the baseline). MRI may be performed instead of CT if a patient cannot tolerate CT contrast agents due to an iodine allergy. An individual patient will be monitored by the same methodology throughout the study. For patients that meet RECIST criteria for complete response or partial response, a confirmatory radiographic assessment will be obtained 4 weeks (+/- 5 days) after the response criteria was met.
- s. Dosing of AK-01 may continue until disease progression if the patient is receiving benefit and is experiencing no severe toxicity in the opinion of the investigator. Following Cycle 1, an entire cycle may be delayed or advanced by +/-1 day for administrative reasons, in which case it will be shortened (or lengthened) by 1 day, respectively.
- t. The discontinuation date will be recorded with the primary reason for discontinuation (if applicable). The patient will attend a Discontinuation visit as soon as possible after participation ceases.
- u. A CT scan and assessment of tumor response will be performed at the Discontinuation visit for patients who discontinue the study for reasons other than radiographic progression, and if a CT scan has not been performed within the prior 4 weeks.

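### SAP 6.1: the second bullet of the PFS missed-scan rule does not require any scan to be missing, so read literally it censors events after about week 22 in fully scanned patients

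*SAP*

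**What the plan says.** The governing sentence in SAP 6.1 (Progression Free Survival) covers progression or death after two or more missing or non-evaluable "consecutive post baseline tumor assessments will be censored at the date of the last adequate tumor assessment before the missed (or not evaluable) tumor assessments". The SAP then turns this into an operational definition: events after two or more "missing assessments are identified as events that meet either of the following". Three bullets follow, and meeting one is enough.

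- Bullet 1: "there was no preceding post-baseline adequate tumor assessment and the event occurred more than 1 week of the last dose in Cycle 4".
- Bullet 2: "the first post-baseline assessment was performed within 1 week of the last dose in Cycle 2 and then the event occurred more than 10 weeks" from the last Cycle 4 dose.
- Bullet 3: "the event occurred more than 19 weeks (2x9 weeks + the allowed assessment window) after the last adequate tumor assessment".

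The scan schedule is in Protocol Appendix 1, footnote r: a CT scan "will occur within 1 week of the last dose of Cycle 2 and Cycle 4, and every 9 weeks" (±1 week) after that, for as long as treatment lasts. The footnote adds: "The schedule of tumor assessments will be maintained independent of any treatment schedule delays or changes". Protocol 5.2.2 fixes the cycle length: "AK-01 will be administered twice daily, every day of a 21-day cycle".

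PFS is exploratory in both phases (SAP 6.2 and 6.3). SAP 9.6.2 analyses it in the Efficacy Evaluable set and promises the Kaplan-Meier median, Q1 and Q3 with 95% confidence intervals.

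**The concern.** Bullet 1 applies only when there is no earlier adequate scan, and bullet 3 counts from the last adequate scan. Each therefore contains a real gap in assessment. Bullet 2 looks only at the first scan and the date of the event. It says nothing about the Cycle 4 scan or the one after it, and no other section supplies that condition.

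A patient who attended every scan can thus be classed as having missed two. The event is turned into a censored observation, and the instruction on where to censor (the last adequate scan before the missed ones) has no answer because none was missed. The rule falls on patients whose first scan was on schedule. It also separates PFS from DOR: the DOR definition in SAP 6.1 has no missed-scan rule, so the same week-30 progression in a responder would be a DOR event and a censored PFS time.

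A second, smaller problem is that bullets 1 and 2 are anchored to the last Cycle 4 dose, a date that does not exist for patients who stop before Cycle 4.

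**Working it through.** **Inputs.** Cycle length is 21 days with continuous dosing (Protocol 5.2.2). Scans are at the end of Cycles 2 and 4, then every 9 weeks, ±1 week (Appendix 1, footnote r). The bullets are those of SAP 6.1.

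**The plan's own figure.** Bullet 3: 2 × 9 + 1 = 19 weeks. This reproduces.

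**Calendar.** End of Cycle 2 = 2 × 21 = Day 42 (week 6). End of Cycle 4 = 4 × 21 = Day 84 (week 12). Later scans are at weeks 21, 30, 39 and so on. The bullet 1 cut is 84 + 7 = Day 91 (week 13). The bullet 2 cut is 84 + 70 = Day 154 (week 22), which is the latest allowed date of the week-21 scan. The Cycle 4 scan window opens at 84 − 7 = Day 77 (week 11).

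**Bullets applied to scan histories (weeks).** Bullet 1 is false in every row because an adequate scan precedes the event. The number after bullet 3 is the gap from the last adequate scan. The last column is the wording proposed under the fix.

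| Adequate scans before event | Event | Two missed? | Bullet 2 as written | Bullet 3 | Bullet 2 reworded |
|---|---|---|---|---|---|
| 6, 12 | PD 21 | no | no | no (9) | no |
| 6, 12, 21 | PD 30 | no | **yes** | no (9) | no |
| 6, 12, 21, 30 | PD 39 | no | **yes** | no (9) | no |
| 6, 21 (12 missed) | PD 30 | no, one | **yes** | no (9) | no |
| 6, 12 (21 missed) | death 23 | no, one | **yes** | no (11) | no |
| 6 (12, 21 missed) | death 24 | yes | yes | no (18) | yes |
| 6, confirmatory 10 (12, 21 missed) | death 24 | yes | yes | no (14) | yes |
| 6, 12 (21, 30 missed) | PD 39 | yes | yes | yes (27) | no |

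The bold entries are wrong flags. The first scheduled scan affected is week 30 (weeks 29–31). Deaths and unscheduled progressions are affected as soon as week 22 has passed.

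Bullet 2 does have a purpose. After a week-6 scan, bullet 3 acts only beyond 6 + 19 = week 25, so bullet 2 is what covers weeks 22 to 25.

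**Size.** The documents give no PFS median, so this is an assumption shown over a range: exponential PFS, an on-time first scan for everyone, full follow-up. Day 154 = 154 / 30.44 = 5.06 months. Share of events after the cut = 2^(−5.06 / median):

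- median 3 months: 2^(−1.687) = 0.31
- median 4 months: 2^(−1.265) = 0.42
- median 6 months: 2^(−0.843) = 0.56

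**Quantiles under the same model.** A quantile is lost if its true value lies beyond 5.06 months.

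- Q3 = 2 × median = 6, 8 and 12 months: lost at all three.
- Median: lost only if it exceeds 5.06 months.
- Q1 = 0.415 × median: lost only if the median exceeds 5.06 / 0.415 ≈ 12.2 months.

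**Check with progression seen only at scans.** Flagged events are then those arising after the week-21 scan, a share of 2^(−21 / median in weeks): 29.7%, 44.5% and 54.5% at medians of 12, 18 and 24 weeks. With a continuous cut at week 22 the shares are 28.1%, 42.9% and 53.0%, so this refinement adds one to two points. A simulation that censors flagged patients at the scan before progression gives a curve with no drop after week 21:

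- At a 12-week median the curve stops at 0.297. The median (12 weeks) is unchanged but Q3 is not reached; the correct curve is at 0.175 by week 30.
- At 24 weeks it stops at 0.545 and the median is not reached; the correct curve passes it at week 30.

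**The case against.** The governing sentence is sound and shows the intent. In bullet 2 the words linking the scan to the event can be read as meaning that nothing came in between. The undefined censoring date would probably make a programmer stop and ask, and SAP 9.1.4 requires independent reprogramming of the efficacy analysis. All of this stands, and it makes the error possible rather than certain. It does not supply the missing condition: two programmers working from the same bullet could share the mistake or disagree.

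The percentages are ceilings with respect to scan adherence and follow-up. Scans run only during treatment. Patients who leave without radiographic progression return to standard care (Protocol 6.7.1). A cohort may be analysed once all its patients have completed 8 cycles (week 24), progressed or stopped (Protocol 8.3), so some late-enrolled patients would be censored before the week-30 scan anyway. This also stands.

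A reader might infer from the missing Cycle 4 date that the rule cannot be evaluated for anyone who stops early. The documents do not support that. Bullet 3 is computable for anyone with an adequate post-baseline scan. Bullet 1 has little reach, because the Efficacy Evaluable set (SAP 8.1) requires such a scan. Patients who merely interrupt dosing stay on the cycle schedule (Appendix 1, footnote b). The anchor matters mainly for bullet 2.

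**Conclusion.** Bullet 2 is wrong as written. It lacks the no-adequate-scan-in-between condition that the other two bullets carry, contradicts the sentence it implements, and leaves the censoring date undefined for patients who missed nothing. Under the stated assumptions, at most about 31%, 42% or 56% of PFS events are exposed at true medians of 3, 4 or 6 months, give or take the one to two points from detection at scans. The upper tail and Q3 go in each case. The median goes only if its true value is above about 5 months.

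Two stronger readings are tempting. One is that all the promised PFS quantiles are biased; Q1 is not, unless the true median exceeds about 12 months, and with a short PFS the median does not move. The other is that the trial's efficacy conclusion is at risk. It is not: PFS is exploratory, no PFS hypothesis is tested, and the ORR test in SAP 9.6.1 does not use this rule. The point should be fixed, preferably before database lock so that no reading is chosen after PFS results are seen, but it does not threaten the primary analysis.

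**What to change.** Correct bullet 2 rather than delete it. Suggested wording: *the last adequate post-baseline assessment before the event (including any confirmatory scan) was before the Cycle 4 scan window opened (planned Day 77), and the event occurred after planned Day 154.* Naming confirmatory scans matters. Footnote r calls for one about 4 weeks after a response, and a condition tied only to the Cycle 2 scan would miss a responder whose last adequate scan was the week-10 confirmation. As the table shows, this wording removes the wrong flags, keeps the cases where the week-12 and week-21 scans were both missed, and leaves later gaps to bullet 3.

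Secondary change: anchor bullets 1 and 2 to the planned end of Cycle 4 (Day 84 counted from the Treatment start date, giving cuts at Days 91 and 154) instead of the last Cycle 4 dose. This fits a scan schedule that does not move with dosing.

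Cost: one SAP sentence, the anchor wording and one derivation, with no new data. The downside is that events after early treatment stop would be judged by calendar time although footnote r schedules scans only during treatment. Bullet 3 already does this.
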